Official Title: Assessing the Safety of Nighttime Passy-Muir Valve Use and its Impact on Sleep Quality in the Long-Term Acute Care Hospital Setting: a Cross-Over Controlled Study

Clinical Trial Number: NCT06229639

Use date of study closeout: 9/1/2016

STUDY PROTOCOL AND STATISTICAL ANALYSIS PLAN

Study Protocol

Eligible participants were inpatients 18 years of age or older, who were admitted to Gaylord Specialty Healthcare following tracheostomy placement during an acute care hospital stay, were eligible for decannulation, and who had a tracheostomy tube size of six or smaller and did not require ventilation assistance. These patients were initially referred to the study by a Respiratory Care Practitioner (RCP). Patients also needed to meet all criteria outlined in Gaylord's decannulation protocol, along with the specific criteria required for the study. (**Table 1**). Eligible patients were then approached for study enrollment. Enrolled participants were given the FDA-approved PMV #2001 for the study. The PMV is a bias-closed, no-leak speaking valve that allows patients to speak at a level consistent with their normal vocalization range.

Participants were monitored and evaluated using the same outcomes and safety metrics typically used during the study site's decannulation protocol. This included an initial and daily evaluation by a Pulmonary or Critical Care Medicine consultant and daily morning arterial blood gas (ABG) measurements by an RCP. The RCP then conveyed ABG measurement to the covering therapists and Pulmonary or Critical Care Medicine consultants at shift change. The RCP then communicated daily with the covering Independent Medical Practitioner (IP). If participants failed to meet the decannulation or study criteria at any point during the protocol, then the IP was notified, and the protocol was to be canceled.

PMV Trial – Study Day One and Night One

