If study day one and night one were successful, the protocol was continued to day two. During day two, participants wore a tracheostomy cap, also known as a plug. If the plug was tolerated without any adverse response, participants were instructed to keep the tracheostomy plug in place throughout the night. Again, nursing staff monitored and recorded heart rate, blood pressure, and temperature every four hours, and the RT on duty recorded oxygen saturation, ET_{CO}₂ levels, and respiratory rate. Same as night one, if any adverse events or acute changes occurred, it was planned that the plug be removed, ventilator support would be started, and the trial considered a failure. If no adverse events occurred upon waking up following night two, the participants were again administered the RCSQ. Once completed, following night two, participants' roles in the study were done and continued with the decannulation protocol as appropriate.

Statistical Analysis

Continuous clinical and demographic characteristics were described with means and 95% confidence intervals, and categorical data were described with frequencies. Differences in categorical variables were evaluated using Fischer's exact test or Chi-Square testing as appropriate. Differences in continuous variables were analyzed using paired t-tests for normally distributed data and Wilcoxon signed-rank test for non-normally distributed data. Two-way ANOVA analysis and Tukey's multiple comparisons post-hoc test were used to analyze differences in continuous variables at three time points (22:00, 02:00, and 06:00). Complete case analysis was performed on the dataset, with only complete pairs of data from night one and night two at the three time points being included in the analysis. All data were analyzed via GraphPad Prism 9 (GraphPad Software, San Diego, CA). Statistical significance was defined as a p-value less than 0.05.

Criteria for Initiation of Decannulation Protocol and Other Study-Specific Criteria

Decannulation Criteria

Afebrile
Hemodynamically stable
Clear or stable chest x-ray
Controlled Secretions
Peak Cough Flow ≥ 160 L / m
Satisfactory on-going nutrition (low risk of aspiration)
No clinical evidence of tracheal obstruction
Ability to tolerate a speaking valve

Inclusion Criteria

Patient has evidence of respiratory insufficiency requiring a tracheostomy tube without current need for assisted ventilation.
Patient will be continuously monitored with telemetry.

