Patient satisfies criteria for the delInitiationcannulation protocol and agrees to use the Passy Muir Valve during sleep.

Patient is able to follow directions following speech, language, and cognitive evaluations, or other screening completed during the Speech-Language Pathologist and physician assessment.

Patient is at least 18 years old.

An informed consent is signed by patient or Power of Attorney (POA).

Patient is able to tolerate the Passy Muir Valve during the day for a minimum of 6 continuous hours.

Patient has a maximum size #6 Shiley cuffless tracheostomy tube or equivalent.

Exclusion Criteria

Patient identified at time of admission as requiring invasive long-term assisted ventilation.

Patient with documented or suspected upper airway obstruction and/or surgery or permanent tracheostomy tube.

Patient is quadriplegic (due to the inability for a quadriplegic patient to manually self-remove the valve in case of emergency).

Patient or POA failed to sign consent.

Patient has a severe cognitive impairment as determined by a formal cognitive-linguistic evaluation by a licensed Speech Language Pathologist.

Patient unable to meet criteria for decannulation protocol or has failed decannulation protocol within last two weeks.

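### The quadriplegia exclusion acts on a diagnosis although its stated reason is inability to remove the valve by hand, and no other listed criterion assesses that ability

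*Combined protocol and SAP*

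**What the plan says.** One item in the Exclusion Criteria bars quadriplegic patients and explains why: "due to the inability for a quadriplegic patient to manually self-remove the valve in case of emergency".

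Three other criteria come nearest to patient ability:

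- Inclusion Criteria: "Patient is able to follow directions following speech, language, and cognitive evaluations, or other screening", done as part of the Speech-Language Pathologist and physician assessment.
- Inclusion Criteria: "Patient is able to tolerate the Passy Muir Valve during the day for a minimum of 6 continuous hours".
- Exclusion Criteria: "Patient has a severe cognitive impairment as determined by a formal cognitive-linguistic evaluation".

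The device differs between the two nights. On night one the participant wears the speaking valve, described under Study Protocol in these words: "The PMV is a bias-closed, no-leak speaking valve". On night two, under Tracheostomy Plug Trial – Day Two and Night Two, "participants were instructed to keep the tracheostomy plug in place throughout the night". Only participants whose first day and night succeeded go on to day two, and no second set of eligibility criteria is given for it.

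**The concern.** The authors give self-removal in an emergency as their reason for keeping a group of patients out, but they act on that reason only through a diagnostic label. A site applying the list literally would enrol a patient who has the same inability from another cause, such as marked weakness of both hands.

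What is at stake is participant protection and a clear description of who was studied. The valve is kept on past the hour at which it would usually come off, so the study itself adds the overnight exposure. Safety of night-time use is the question in the title, and a reader applying the result elsewhere would want to know whether participants could take the device off themselves.

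**Working it through.** The plan gives no figure on this point, so the check is a comparison of text.

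**1. Does any other criterion test the stated function?** The lists hold 8 decannulation, 8 inclusion and 6 exclusion items: 8 + 8 + 6 = 22.

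| List | Subjects covered | Ability to remove a device by hand |
|---|---|---|
| Decannulation (8) | temperature, haemodynamics, chest x-ray, secretions, cough flow, nutrition and aspiration risk, tracheal obstruction, valve tolerance | not addressed |
| Inclusion (8) | respiratory status, telemetry, decannulation criteria and agreement to wear the valve asleep, following directions, age, consent, 6-hour valve tolerance, tube size | not addressed |
| Exclusion (6) | long-term ventilation, upper airway obstruction or permanent tube, quadriplegia, consent, severe cognitive impairment, decannulation protocol not met or recently failed | quadriplegia item only, by diagnosis |

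One of the 22 items concerns self-removal. The item on following directions rests on speech, language and cognition. The 6-hour item shows that the patient can wear the valve, not that the patient can take it off. Eligibility under Study Protocol (age, tube size, no ventilation, referral) adds nothing on hand function.

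**2. What follows for a non-quadriplegic patient who cannot remove the device?** If the other criteria are met, no listed item excludes this patient. The stated reason applies but the rule does not.

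**3. Which nights does the exclusion govern?** It is applied to the person at enrolment, and night two is open only to those who completed night one. Quadriplegic patients are therefore kept out of both nights. What is missing is narrower: the reason mentions the valve alone, and none of the 22 items mentions removing the plug.

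**4. What else protects the participant?** Telemetry is continuous. The respiratory therapist on duty records saturation, end-tidal CO₂ and respiratory rate, with no interval stated. Device removal is planned whenever a serious reaction occurs, and is not tied to charting times. The text does not say who removes the device.

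**5. How many patients are affected?** The documents give no data on upper-limb function and no sample size, so no number can be derived.

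**The case against.** The strongest objection is that the protocol never requires every participant to be able to self-remove. It gives a reason for excluding one group, and elsewhere plans removal without making it depend on the participant. With the monitoring described, self-removal may be only a back-up. This stands in part: calling it a safeguard the protocol deems necessary for everyone would be an inference. However, telemetry is itself an inclusion criterion, and the authors still excluded patients on grounds of self-removal. By their own reasoning, monitoring did not make that concern redundant.

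A second objection is that a bedside check may exist in the site's full decannulation protocol or in the screening assessment. The documents do not show the full site protocol, and Table 2 and Figure 1 are not visible, so this cannot be ruled out. If such a check exists, citing it in the criteria settles the point.

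A reader might also infer several stronger claims that the documents do not support:

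- **That the plug night is uncovered.** The exclusion operates at enrolment, so it covers that night.
- **That participants are unprotected for four hours at a time.** The four-hour interval belongs only to the nursing readings of temperature, blood pressure and heart rate.
- **That both devices occlude the tracheostomy.** The word fits the plug; the valve is described as a bias-closed speaking valve.
- **That the safety comparison is distorted.** Comparisons are paired within participant, hand function would ordinarily be the same on two consecutive nights, and no mechanism for a distortion is apparent.
- **That quadriplegic patients with working hands should be admitted.** The reason may not fit such patients, but admitting them would relax an existing safety exclusion, which is debatable. Closing the gap does not need it.

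**Conclusion.** The point holds as a mismatch between an eligibility rule and its own stated reason. As written, the criteria admit non-quadriplegic patients who cannot remove the device by hand, and they say nothing about removing the plug. The matter is relevant to safety and cheap to correct, and the documented monitoring mitigates it in part. Its size in patients is unknown. Type I error, power and the planned analyses are not affected. The conclusion assumes that the listed criteria are the complete eligibility rules and that no unseen site procedure already checks self-removal.

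**What to change.** Reconcile the exclusion with the reason it gives. Keep the quadriplegia item and extend it to any patient unable to remove the valve by hand. The study team should decide whether the same wording is to cover the plug, and should state that decision. The ability can be observed during the assessment by the Speech-Language Pathologist and physician that the Inclusion Criteria already require.

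The cost is a sentence of eligibility wording and a brief observation within an existing visit. The downside is that a few patients with poor hand function become ineligible.

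The document carries a study closeout date of 9/1/2016, so enrolment cannot be changed. For this study, the report should state whether any participant could not self-remove the valve or the plug, or that this was not assessed. The reconciled wording should be used if the protocol is reused.
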